## REVISION HISTORY

Revision #	Version Date	Summary of Changes	Consent Change?
02	01/21/2019	Extend enrollment to 9-5 pm	N
03	06/04/2019	Extend enrollment to 24 hours/ day, 7 days per week	N
04	07/20/2020	Addition of e consent. Addition of MD to those who may administer Lumason	N

## 1.0 Study Summary

Study Title	The Role of Contrast Enhanced Ultrasound to Diagnose Children with Appendicitis
Study Design	Single institution non-randomized clinical trial
Primary Objective	Determine the efficacy of contrast enhanced ultrasound (CEUS) in improving the diagnosis of acute appendicitis in children
Secondary Objective(s)	
 
• Utility of CEUS in making a definitive diagnosis of acute appendicitis
 
• Utility of CEUS in decreasing Rates of CT scan utilization
 
• Outcomes of patients who undergo CEUS for appendicitis
 
• Negative appendectomy rates
 
• Costs
 

Research Intervention(s)/Investigational Agent(s)	Lumason (sulfur hexafluoride lipid-type A microspheres) injectable suspension
IND/IDE #	N/A
Study Population	Children between the ages of 8 and 17
Sample Size	250 subjects
Study Duration for Individual Participants	30-60 minutes
Study Specific Abbreviations/Definitions	
CEUS- contrast enhanced ultra sound      CT- computed tomography      MRI- magnetic resonance imaging      CMH- Children's Mercy Hospital      DSDR- Department of Surgery Data Repository      DOB- date of birth      MRN- medical record number      OSH- outside hospital      PAS- pediatric appendicitis score      LAR- legally authorized representative      IV- intravenous      PI-principal investigator      ICU- intensive care unit      P/A- permission/assent      ED Emergency Department

## 2.0 Objectives

- 2.1 The main objective of this study is to determine the efficacy of Contrast Enhanced Ultrasound (CEUS) in improving the diagnoses of acute appendicitis in children.
- 2.2 We hypothesize that CEUS can be used effectively to make a definitive diagnosis when gray-scale ultrasound is inconclusive.

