## 4.0 Study Endpoints

4.1 The primary endpoint is the proportion of patients for whom the appendix is enhanced by CEUS when using the same diagnostic criteria as gray scale ultrasound. Lumason will be considered effective if the sensitivity of grayscale ultrasound is enhanced in more than 50% of images as determined by the blinded interpreting pediatric radiologist.

Secondary endpoints include:

- Utility of CEUS in making a definitive diagnosis of acute appendicitis
- Utility of CEUS in decreasing rates of CT scan utilization
- Negative appendectomy rates

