5.3 N/A

## 6.0 Procedures Involved

- 6.1 This will be a single-center non-randomized trial that will add to our institution's current diagnostic algorithm one CEUS to subjects whom are clinically suspicious for acute appendicitis. Currently, a gray-scale abdominal ultrasound is performed to help establish the diagnosis. When the results of the gray-scale abdominal ultrasound are inconclusive, the treating physician may choose to refer the patient for a CT scan in order to establish a definitive diagnosis. Our study does not look to alter that process.
- 6.2 For those who consent to study participation, we propose obtaining a CEUS after the initial gray-scale ultrasound. Once the initial ultrasound is complete, the contrast Lumason® (sulfur hexafluoride lipid type-A microspheres) will be administered through an already existing IV catheter by an MD, RN or a radiology technologist trained and certified to administer the Lumason® contrast agent, and

an abdominal scan will be completed. The patient will then continue with standard of care treatment per his treating physician. The CEUS image will be read at a future time by a CMH radiologist blinded to the results of the gray scale ultrasound and CT if one was obtained as these will be used for comparison.

6.3

- Lumason will be administered by radiology personnel (radiologist, US technologist, or Sedation RN). Subjects will be monitored during the entirety of the procedure. Once the study procedure has been completed, patients will continue to go through the standard of care process and return to the ED (Emergency Department) or floor while they await the results of their gray-scale ultrasound and CT, if one was obtained. ED/ floor staff will continue to monitor patients for any adverse events.
- Lumason (sulfur hexafluoride lipid-type A microspheres) is the investigational product. The recommended dose of Lumason for children is 0.03 mL/kg up to a maximum dose of 2.4mL injected into a peripheral intravenous catheter. See individualization of dose below.

1. Follow the Lumason injection with a flush of 5 ml of 0.9% Sodium Chloride Injection, USP.
2. The maximum total dose for children as listed in the package insert should not exceed 2.4 mL in any 10-minute period. For this study, over any 10-minute period we intend to administer the approved dose of 0.03 mL/kg up to a maximum of 2.4 mL.

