## **25.0 Permission/Accent/Consent Process**

25.1 Permission/assent will be obtained on all subjects wishing to participate.

- The p/a process will take place in the ED at the patient's bedside.

- While eligible candidates will be given all necessary information to make an informed decision and will have every opportunity to ask questions, the waiting period available between informing the prospective subject and obtaining p/a will be limited as this study does not intend to delay standard of care treatment. A potential subject who has not affirmatively signed the p/a form prior to the standard gray scale ultrasound will continue through SOC treatment without prejudice.
- We will be following CMH research policies on informed consent.
- We will not be obtaining permission/assent via telephone as such is not feasible for this study.
- This pediatric research study will be conducted entirely in the state of Missouri and will involve enrolling minors under the age of 18.
- Parental permission will be obtained from one parent or LAR.
- Other than biological parents, LARs such as an adoptive parent will be allowed to consent for a child's participation in this study.
- Assent will be obtained from all children participating in this study unless the study team member attempting to obtain P/A determines the child is not capable of providing assent.
- The child's assent will be documented on the combined P/A form.
- In the event assent may not be obtained, the reason(s) will be documented in the provided section of the P/A form.

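### The only success rule (Protocol 4.1) pools all enrolled children and counts enhancement, so it does not test hypothesis 2.2, which concerns a definitive diagnosis after an inconclusive gray-scale scan

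*Protocol*

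**What the plan says.** Section 2.1 of the Protocol sets the main objective as the "efficacy of Contrast Enhanced Ultrasound (CEUS) in improving the diagnoses of acute appendicitis in children", with no restriction by gray-scale result. Section 2.2 then gives the one stated hypothesis: "CEUS can be used effectively to make a definitive diagnosis when gray-scale ultrasound is inconclusive".

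Section 4.1 defines the primary endpoint as the proportion of patients whose appendix is enhanced, and adds the only criterion for success: "Lumason will be considered effective if the sensitivity of grayscale ultrasound is enhanced in more than 50% of images". The first secondary endpoint in the same section is "Utility of CEUS in making a definitive diagnosis of acute appendicitis", with no population attached.

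Section 6.1 describes current practice: "When the results of the gray-scale abdominal ultrasound are inconclusive, the treating physician may choose to refer the patient for a CT scan". Section 6.2 says that, for those who consent, "we propose obtaining a CEUS after the initial gray-scale ultrasound". It continues: "The CEUS image will be read at a future time by a CMH radiologist blinded to the results of the gray scale ultrasound", and also blinded to any CT, because both are to serve as comparators.

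Section 11.0 has no criterion on the gray-scale result. Section 25.1 places permission and assent before that scan: a candidate who has "not affirmatively signed the p/a form prior to the standard gray scale ultrasound will continue through SOC treatment".

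**The concern.** The hypothesis fixes an outcome (a definitive diagnosis) and a population (children with an inconclusive gray-scale scan). The rule that decides whether Lumason is effective shares neither. Followed as written, the trial can declare the agent effective, or not effective, without having tested its hypothesis.

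The inconclusive group is also the one section 6.1 singles out as the point where a CT may follow. A verdict drawn from all children could be taken as an answer for that group when it is not one.

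**Working it through.** The protocol gives no figure on this point, so there is nothing to reproduce. The check compares the texts and then illustrates the consequence with arithmetic.

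**Step 1. Population and outcome side by side.**

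| Place | Population | Outcome | Success criterion |
|---|---|---|---|
| 2.1 main objective | children, unrestricted | improved diagnosis | none stated |
| 2.2 hypothesis | inconclusive gray scale | definitive diagnosis | none stated |
| 4.1 primary endpoint and rule | patients / images, unrestricted | enhancement | more than 50% |
| 4.1 first secondary endpoint | not named | definitive diagnosis | none stated |

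The rule matches 2.1 in population. It matches 2.2 in neither column. The secondary endpoint matches 2.2 in outcome only.

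**Step 2. Who is counted under the rule.** Section 4.1 does not say that all enrolled children are counted; this follows from three other places. Permission precedes the gray-scale scan (25.1), so enrolment cannot depend on its result. No eligibility criterion concerns that result (11.0). CEUS is proposed for everyone who consents (6.2). Conclusive and inconclusive scans are therefore pooled.

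**Step 3. Can the pooled rate hide the subset?** Inputs: N = 250 (13.1; section 20.2 says up to 250) and the threshold of more than 50% (4.1), which means at least 126 of 250. Assumptions: exactly 250 children, one image per child (4.1 counts images), and an inconclusive share *f* that the protocol does not give, taken as 10% to 50%.

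If no inconclusive scan is enhanced, the rate needed among conclusive scans is 126 / (250 × (1 − *f*)).

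**Step 4. Precision in the subset.** At a true rate of 50%, the 95% half-width is 1.96 × √(0.25 / *n*), with *n* = 250 × *f*.

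| *f* | Inconclusive *n* | Conclusive *n* | Conclusive rate that still meets the rule | 95% half-width in the subset |
|---|---|---|---|---|
| 10% | 25 | 225 | 126/225 = 56% | 19.6 points |
| 20% | 50 | 200 | 126/200 = 63% | 13.9 points |
| 30% | 75 | 175 | 126/175 = 72% | 11.3 points |
| 40% | 100 | 150 | 126/150 = 84% | 9.8 points |
| 50% | 125 | 125 | 126/125 > 100%, impossible | 8.8 points |

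For all 250 the half-width is 1.96 × √(0.25/250) = 6.2 points.

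Step 3 takes the extreme of zero enhancement in the subset. It shows that a pooled rate can conceal a subset. It does not measure definitive diagnosis, which is the outcome in 2.2.

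**The case against.** The strongest reply has three parts.

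First, the primary endpoint serves main objective 2.1, and its population is right for that. This stands, and the primary proportion should stay.

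Second, the secondary endpoint may be meant as the endpoint for 2.2. Section 6.1 also uses the idea of a definitive diagnosis for children sent to CT after an inconclusive scan, so the population could be implied. This is a fair reading. The endpoint is unrestricted by omission; it is not expressly defined on all children. The gap is under-specification and not a contradiction, but it leaves 2.2 without an analysis tied to its population.

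Third, subset definitions and report categories commonly belong in a statistical analysis plan, which may exist and is not at hand. This stands for the detail. It does not remove the mismatch, because the hypothesis and the declaration of effectiveness are both fixed in the protocol.

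Two stronger readings are tempting and are not supported:

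- From section 20.1, which correlates operative findings with the gray-scale read, a reader might infer that CEUS reads in inconclusive cases are never checked. Section 6.2 plans to compare the CEUS read with gray scale and with CT where obtained, and CT may follow an inconclusive scan. Part of the group is therefore checked.
- A reader might infer that the pooled and subset results agree only if CEUS performs alike in both groups. Verdicts can agree at different rates: 60% in one group and 80% in the other both exceed 50%. Nor would equal enhancement rates make the rule answer 2.2, because enhancement is not a diagnosis.

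**Conclusion.** The point holds as a mismatch within the protocol: the only success rule does not test the only stated hypothesis, in population or in outcome. It rests on the text of 2.2, 4.1, 6.2, 11.0 and 25.1 and needs no assumed figure.

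How far the pooled result would mislead is unknown, because the protocol gives neither the inconclusive share nor any expected rates. The range of 56% to 84% is an extreme illustration under the assumptions listed above, and at a share of 50% or more that extreme cannot occur. The trial remains workable and the data needed are already to be collected, so this should be corrected but does not undermine the primary analysis for 2.1.

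**What to change.** Leave enrolment, consent and the all-enrolled primary proportion as they are, for objective 2.1. Add to section 4.1:

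- The definitive-diagnosis endpoint is analysed for hypothesis 2.2 in children whose original gray-scale report is classified as inconclusive before the CEUS read. The report categories that count as inconclusive and as definitive are named. Someone other than the CEUS reader does the classification, so that the blinding in 6.2 is kept.
- The result is the proportion with a definitive CEUS read and its 95% CI, together with agreement of those reads with CT (already planned in 6.2), pathology or operative findings where available.
- No conclusion on 2.2 is based on the all-enrolled proportion, and the 50% threshold is not carried over to this measure without a justification.

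The cost is a short addition to the text and one classification per gray-scale report. It is feasible because the CEUS images are read later (6.2) and the imaging, pathology and operative findings are already recorded (6.4). No further scans or consent are needed.

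There are two drawbacks. The estimate is less precise, with a half-width of about 20 points if 10% of scans are inconclusive and about 9 if 50% are. Agreement is also only partially verified: children with neither surgery nor CT drop out, so negative CEUS reads are checked least. Agreement should therefore be reported as descriptive, with the number of unverified children shown.

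Rewording 2.2 to cover all enrolled children and to concern enhancement would be cheaper and would remove the mismatch, but it would leave the question in 2.2 unanswered.

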## 3.0 Background

- 3.1 Pediatric appendicitis represents the most common pediatric abdominal surgical disease with the highest incidence found in children aged ten to 19 years old (1). The diagnosis of appendicitis commonly consists of a thorough history, physical exam and laboratory evaluation along with diagnostic imaging. With both a high sensitivity and specificity, CT scan remains the most commonly used imaging modality for diagnosis (2). With reports in the literature showing the adverse effects of radiation exposure in children from computed tomography (CT) imaging (3, 4), alternative methods to diagnose acute appendicitis have been applied including Magnetic Resonance Imaging (MRI) (4) and ultrasound (US). MRI eliminates ionizing radiation when compared to CT however, its widespread use is limited due to its high cost, limited availability and the potential need for sedation in young children. Trans-abdominal ultrasound is widely available and also eliminates ionizing radiation but is user dependent. The utilization of CEUS to enhance the diagnostic capabilities for appendicitis is a novel alternative to CT imaging.
- 3.2 A recent report in the literature demonstrates the effective use of CEUS to evaluate blunt solid organ injuries in children with abdominal trauma (5).

In Europe, CEUS using SonoVue, the European brand-name for Lumason, has been used clinically for more than a decade, reported mainly in adults. Valentino, et al. published results of a prospective study performed in Italy comparing the sensitivity and specificity of ultrasound and CEUS to abdominal/pelvis CT with IV contrast. A total of 27 patients were prospectively studied and they found CEUS to have a 92.9% sensitivity, 100% specificity, 100% positive predictive value (PPV) and 93.8% negative predictive value (NPV) compared to CT (6). Valentino published a subsequent study of 133 adult trauma patients with blunt abdominal solid organ injury on CT who underwent CEUS and found 96.4% sensitivity, 98% specificity, 98.8% PPV and 94% NPV (7) compared to CT.

Lumason is now FDA-approved for echocardiography in adults, characterization of liver lesions in both the adult and pediatric population, and vesicoureteral reflux in pediatrics.

- 3.3 The potential use of CEUS to diagnose pediatric appendicitis remains unknown. The goal of this trial is to determine the utility of

CEUS to enhance diagnostic capabilities in children with suspected appendicitis. We hope that our study will give physicians an added diagnostic tool for children with abdominal pain.

## 4.0 Study Endpoints

4.1 The primary endpoint is the proportion of patients for whom the appendix is enhanced by CEUS when using the same diagnostic criteria as gray scale ultrasound. Lumason will be considered effective if the sensitivity of grayscale ultrasound is enhanced in more than 50% of images as determined by the blinded interpreting pediatric radiologist.

Secondary endpoints include:

- Utility of CEUS in making a definitive diagnosis of acute appendicitis
- Utility of CEUS in decreasing rates of CT scan utilization
- Negative appendectomy rates

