**13.0 Local Number of Subjects**

*13.1 This study will enroll 250 subjects. Assuming an accrual rate of 15-20 subjects per month, we estimate it will take 12-15 months to complete enrollment.*

*13.2 Based on prior data, approximately 375 children are diagnosed with appendicitis at our institution per year. We plan to screen up to 750 potential subjects for eligibility over the course of the study.*

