## 20.0 Data Management and Confidentiality

20.1 The captured CEUS images will be evaluated by a single Children's Mercy Hospital pediatric radiologist to determine and establish a pattern compared to the standard gray scale ultrasound report. This radiologist will be blinded to the final reads from the gray scale reports. For the children who meet the criteria of appendicitis, they will be followed post-operatively to confirm and correlate the intra-operative findings with the gray scale read.

Descriptive analysis of demographics and patient-level data will be performed using STATA. Direct comparisons will be made with parametric or nonparametric measures depending on the distribution of the data.

- 20.2 This study will be made up of a convenience sampling of children presenting to the CMH Adele Hall emergency department with concerns for appendicitis. Enrollment will consist of up to 250 participants.
- 20.3 All data will be entered into a REDCap database that is accessible only to researchers named on the study. Data will be stored on the CMH secure network. The list of chart identifiers which meet inclusion criteria along with dates of birth will be maintained separately from data that will be used for analysis. Each chart will be reviewed by research staff and data entered directly into the research records. The researchers alone will have full access to the data; we will assign a study ID to the medical records in order that we can reference our information during the course of our research. A master list linking Study ID to MRN, Name and other identifiers will be kept separately from the study data, and accessible only to the study team.
- 20.4 N/A
- 20.5 All data will be entered into a REDCap database that is accessible only to researchers named on the study. Data will be stored on the CMH secure network. The list of chart identifiers which meet inclusion criteria along with dates of birth will be maintained separately from data that will be used for analysis. Each chart will be reviewed by research staff and data entered directly into the research records. The researchers alone will have full access to the data; we will assign a study ID to the medical records in order that we can reference our information during the course of our research. A master list linking Study ID to MRN and other identifiers will be kept separately from the study data, and accessible only to the study team.

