## 21.0 Provisions to Monitor the Data to Ensure the Safety of Subjects

This study proposes a one-time intervention of CEUS. Subjects will be monitored in real time at the time of and following the CEUS. Data collected will be evaluated after the first 10 subjects are enrolled.

- All data collected on subjects who receive study drug will be analyzed for safety. The proportion of patients with specific adverse events will be reported as well as the worst grade observed across all adverse events. The maximum confidence interval width for these estimates is 16.8%. If the observed estimated adverse event proportion is 10%, the 95% confidence interval is (5.3,15.6%).
- Safety information will be collected at the time of study visit when the patient is monitored during contrast administration.
- Safety data collection will begin with the first participant. Participants will be monitored in real time.
- The PI or an assigned co-investigator will be responsible for monitoring the data.
- Cumulative data will be reviewed on a weekly basis beginning with the first study participant.
- All data collected on subjects who receive study drug will be analyzed for safety. The proportion of patients with specific adverse events will be reported as well as the worst grade observed across all adverse events. The maximum confidence interval width for these estimates is 16.8%. If the observed estimated adverse event proportion is 10%, the 95% confidence interval is (5.3,15.6%).
- Any adverse event resulting from the contrast agent requiring an ICU admission will trigger an immediate suspension of the research.

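### Section 4.1 declares Lumason effective on a bare proportion above 50%, with no allowance for sampling error; counting children, 126 of 250 is enough (exact 95% CI 44.0–56.8%)

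*Protocol*

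**What the plan says.** Protocol section 4.1 defines the endpoint and then the decision. The endpoint sentence counts children: "The primary endpoint is the proportion of patients for whom the appendix is enhanced by CEUS". The decision sentence counts images: "Lumason will be considered effective if the sensitivity of grayscale ultrasound is enhanced in more than 50% of images". The judgement is made by a radiologist who reads blinded. Nothing else qualifies the decision.

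The other relevant sections do not add a qualification:

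- Section 6.1 describes a single-centre, non-randomised study in which each subject has one contrast-enhanced ultrasound (CEUS).
- Section 13.1 sets the sample size at 250. Section 20.2 makes that a ceiling: "Enrollment will consist of up to 250 participants". No derivation is given.
- Section 20.1 plans descriptive analysis and unspecified parametric or nonparametric comparisons. It does not mention the 50% threshold.
- Section 21.0 gives 95% confidence intervals, but only for adverse event proportions.

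**The concern.** Section 4.1 holds the only criterion in the protocol for the primary conclusion. As written, it compares the proportion the radiologist finds with 50% and stops there. A proportion from at most 250 children carries sampling error of several percentage points, so a result just over the line does not show that the true proportion is over the line. Followed exactly, the rule could lead to a report that Lumason is effective when the data are also compatible with a true rate clearly below one half. Section 3.3 says the potential of CEUS in pediatric appendicitis is unknown, and no expected rate is stated, so a result near 50% cannot be ruled out in advance.

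**Working it through.** **Inputs.** Threshold: more than 50% (section 4.1). Number of children: 250, the best case (sections 13.1 and 20.2). One assessment per child: the endpoint sentence of 4.1 and the single CEUS in 6.1. Assumptions not in the protocol: all 250 are evaluable, and a true 50% is the boundary of not effective.

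**The plan's own figure.** The 250 cannot be reproduced, because no expected proportion, null value, alpha or power is stated. There is no stated error rate for the rule to check against.

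**Step 1: smallest qualifying count.** 250 × 0.50 = 125, so the first count above 50% is 126, and 126/250 = 50.4%.

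**Step 2: exact (Clopper–Pearson) 95% interval for 126/250.**
- Lower limit = 2.5% quantile of Beta(126, 125) = 44.0%.
- Upper limit = 97.5% quantile of Beta(127, 124) = 56.8%.

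The Wilson interval, as a check, is 44.2% to 56.5%.

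**Step 3: smallest count whose exact 95% lower limit exceeds 50%.** The lower limit is the 2.5% quantile of Beta(x, 251 − x). At x = 140 it is 49.6%; at x = 141 it is 50.01% (upper limit 62.6%). So 141/250 = 56.4% is needed. Counts from 126 to 140 (50.4% to 56.0%) satisfy section 4.1 although their interval includes 50%.

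**Step 4: chance of declaring effectiveness.** With X binomial(250, p), compute P(X ≥ 126) for the present rule and P(X ≥ 141) for the bounded rule.

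| True proportion p | Present rule (≥126) | Bounded rule (≥141) |
|---|---|---|
| 45% | 4.9% | – |
| 48% | 24.3% | 0.5% |
| 50% | 47.5% | 2.5% |
| 55% | 93.6% | 35.2% |
| 60% | 99.9% | 89.0% |
| 65% | at least 99.9% | 99.8% |

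The 45% row also shows what the present cut-off amounts to at 250 children: a one-sided 5% test against about 45%.

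**Step 5: fewer evaluable children.** The bare rule is met at 101/200 (exact 95% CI 43.4% to 57.6%) or 76/150 (42.4% to 58.9%), so the interval widens.

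**The case against.** The strongest reply is that 4.1 only names a threshold, and that how a proportion is tested against a threshold is normally left to the statistical analysis plan, which is not available here. That would hold if 4.1 were silent on the decision. But it states the decision in full. An analysis plan that required a confidence bound would conflict with it: 130/250, for instance, would be effective under the protocol and not under the analysis plan.

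The second reply is that the 47.5% is an error rate only if 50% is the null value, which the protocol does not say. This stands. The rule is not shown to be invalid; its reference value and error rate are unstated. With a reference of about 45%, the same cut-off would be a conventional one-sided 5% test.

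The third is that the problem is local. At 250 children and a true 60% or more, the present and bounded rules mostly agree (99.9% against 89.0% at 60%). This also stands.

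A reader might infer more than the protocol supports in two ways.

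- **A much smaller denominator.** Read literally, sensitivity would count only children with appendicitis, and the hypothesis in 2.2 concerns the case where "CEUS can be used effectively to make a definitive diagnosis when gray-scale ultrasound is inconclusive". It is tempting to derive a number of cases from 13.2: "approximately 375 children are diagnosed with appendicitis at our institution per year. We plan to screen up to 750 potential subjects". But the 375 are all diagnoses at the institution, not restricted to the ages and other criteria of section 11.0. The 750 are screened over the whole study, not over a stated number of months, and section 20.2 describes a convenience sample. The number with inconclusive gray-scale scans is not given at all. No figure for a reduced denominator can be supported.
- **Several correlated images per child.** Section 20.1 uses the plural: "The captured CEUS images will be evaluated by a single Children's Mercy Hospital pediatric radiologist". That plural may simply run across children; 6.1 gives each subject one CEUS, and 6.2 speaks of the CEUS image in the singular. Clustering within a child is not established.

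**Conclusion.** The concern holds in a limited form. Section 4.1 fixes the efficacy decision as a bare cut-off, and the protocol nowhere adds a bound, a null value or an alpha. With the child as the unit and all 250 evaluable, 126/250 meets the rule, although the exact 95% interval extends down to 44.0%. Taking 50% as the boundary of not effective, which is an assumption, the chance of declaring effectiveness is close to one half when the true rate sits on that boundary and about one in four at 48%. The consequence is confined to true rates near 50%. It should not be read as a proven 47.5% false-positive rate for the trial.

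**What to change.** First use the child as the unit in both sentences of 4.1, so that the decision refers to the proportion the endpoint defines. Then choose one of the following.

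**(a) Add a bound.** For example: *CEUS will be considered effective if the lower limit of the exact two-sided 95% confidence interval for the proportion of children meeting the primary endpoint, each child counted once and assessed by the blinded radiologist, is above 50%.* This needs at least 141/250 if all are evaluable, and should be recomputed for the number evaluable. It requires no added enrolment but raises the observed proportion needed from 50.4% to 56.4%. At 250 children the chance of success falls from 93.6% to 35.2% at a true 55% and from 99.9% to 89.0% at 60%; at 65% it is 99.8%. A true rate of about 58.8% is needed for an 80% chance, so an expected rate should be stated to judge whether 250 is enough.

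**(b) Make 50% descriptive.** State that 50% is a benchmark, report the proportion with its 95% interval, and do not declare effectiveness from it. This changes only the wording of the conclusion.

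If 50% is meant as an observed cut-off against a lower unacceptable rate, the protocol should state that rate and the alpha. That too is a wording change.
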